6.3. Primary endpoint

• Utility Scores for risk-reducing hysterectomy

6.4. Secondary endpoints

- Variables predictive for risk-reducing hysterectomy
- Cost-effectiveness: incremental cost effectiveness ratio (ICER) per QALY (ICER/QALY) of risk reducing hysterectomy (with and without bilateral salpingo-oophorectomy)
- Endometrial cancer risk threshold for undergoing risk-reducing hysterectomy
- Acceptability of risk-reducing hysterectomy and other preventive options to women in the general population and different EC risk thresholds

7. Study design

This study will consist of 3 parts:

- Part 1 will involve recruitment of women with LS, who will be sent questionnaire 1 to complete on paper/ online. This is a cross-sectional survey of women with LS, designed to determine the HRUS of pre and postmenopausal women undergoing RRH-BSO.
- Part 2A will consist of the development of questionnaire 2, which is designed to determine the HRUS of women at increased risk of EC (but not other cancers) undergoing RRH alone (without BSO). This will involve collaboration with patient and clinical experts to develop a vignette-based questionnaire.

Following development and refinement of this questionnaire, a substantial amendment will be submitted for permission to use this questionnaire amongst a sample of the general population (part 2B).

Following results from parts 1 and 2, health economic modelling using cost-utility analysis will take place. This will determine the lifetime EC risk at which preventive interventions (including RRH and others) are clinically and cost-effective.

 Part 3A will consist of the development of questionnaire 3, which is a vignette-based study, designed to determine the prospective acceptability of RRH for EC prevention in women from the general population, at differing levels of EC risk (with exact levels to be determined by health economic modelling described above.

Following development and refinement of this questionnaire, a substantial amendment will be submitted for permission to use this questionnaire amongst a sample of the general population (part 3B).

Recruitment to each part of the study would be separate, and is described for each part below. Each participant will only be asked to complete one questionnaire at one time point.

Study flow charts for all 3 parts are given in section 9.5. A flowchart for part 1 is given in section 9.5.1, for part 2 in section 9.5.2, and for part 3 in section 9.5.3.

7.1. Part 1

Design: Cross-sectional cohort survey study.

A study flow chart is shown in section 9.5.1.

Screening and recruitment

Please see section 8 for inclusion/ exclusion criteria.

Potential participants will be identified by their treating clinicians through established NHS clinics and databases. This will include Familial Cancer/ Family History/ Cancer genetics Clinics within relevant clinical departments like Gynaecological Oncology and NHS Regional genetics services. Potential participants with LS who meet inclusion criteria will be identified by their usual treating clinicians (the central PRESCORES research team will not have access to this information). Potential participants will also be identified through established relevant research cohorts e.g. the CAPP study and LS registries (e.g. St Marks registry). The researchers on these trials will identify patients who meet the inclusion criteria (the PRESCORES research team will not have access to this information).

Potential participants will also be informed of the study through patient and support groups and charities (for example Lynch Syndrome UK and the Eve Appeal). These organisations may advertise the study on websites or via established mailing lists, and may include electronic links to the PRESCORES website and the study.

Patients identified via treating clinicians or established research studies will be provided with a cover letter (cover letter 1) and the PIS (PIS-1), in either paper or electronic form. Paper and electronic versions will be identical in substance, except for minor differences in instructions relating to the format. This may in person in the clinic, or via post or electronic communication.

Individuals who have seen information about the study disseminated by charities will be able to follow a link to the study website. Individuals who receive the study information in paper form will also be able to follow a link to the study website if they prefer to complete the study electronically. Visitors to the study website will be required to complete a short screening questionnaire (screening questionnaire 1) to determine their eligibility. They will then be able to view PIS-1 and continue on to the consent form and questionnaire.

Consent

Participants are required to complete the study consent form (Study Consent Form Part 1) to participate (on paper/online).

An optional Consent form B is enclosed, which allows participants to provide their contact details if they would like to be informed by our team of any future opportunities to participate in research. Any future research would need separate ethical approval. Completing this form does not compel the participants to become involved in any other research. Completion of this form is not a requirement of the PRESCORES research project. It is stressed that this form is optional, and participants should not complete this if they do not want to be informed about future research. If they are willing to be informed, they may complete this form, and enclose it in the freepost self-addressed envelope with the study consent form and questionnaire 1.

Data collection

After completion of the study consent form, participants will be able to complete questionnaire 1, on paper/electronically. Questionnaire 1 is a survey of women with LS, designed to determine the HRUS of pre and post-menopausal women undergoing RRH-BSO. More information on questionnaire 1 is given in section 7.4.1.

Participants will be able to complete this at a time and place of their choosing. Those who receive the paper PIS-1 but prefer to complete the consent form and questionnaire electronically will be able to follow a link in PIS-1 to the survey website.

Participants will be asked to post completed paper Study Consent Form part 1 (required), consent form B (optional), and Questionnaire 1 (required) back to the study team via an enclosed freepost return envelope. This ends the participant's involvement in the PRESCORES study. Consent forms for those participants consented in clinic can be collected at that time. The participants will be able to complete the questionnaire 1 at a time of their choosing and return by freepost as appropriate.

The completed paper consent form(s) and questionnaire will be returned via enclosed freepost envelope to the central PRESCORES research team at Queen Mary University of London. The PRESCORES research team will retain the questionnaire and optional consent form B, and post consent form 1 to sites. Completed paper consent form 1 will be securely stored at participating sites. Completed paper questionnaires and optional consent form B will be securely stored at Queen Mary University of London.

Data from electronically completed consent forms and questionnaires will be held securely on servers hosted by Queen Mary University of London. Please see section 13 for further information on data collection, management and storage.

Duration of participation

The duration of participation in this study will consist of the time required to read the study information including the PIS-1 and consent form(s), and the completion and return of the consent form(s) and questionnaire 1. After this there will be no further involvement of these participants in this study.

7.2. Part 2

Design: Development of a vignette-based cohort survey study

This part of the study is designed to generate one or more vignettes which represent a **pre-menopausal patient undergoing risk-reducing hysterectomy without bilateral oophorectomy**, for raised endometrial cancer risk (without additional cancer risk at other sites). These vignettes are intended to be valued by participants using EQ-5D. The development process follows methodological recommendations from NICE and other authors (53, 54).

A flowchart for part 2 is given in section 9.5.2.

7.2.1. Part 2A: Development of Questionnaire 2

Vignette development will be informed by a review of published literature on qualityof-life following similar surgery (including quantitative and qualitative studies), and any other published sources of information such as from established medical organisations, or charities.

Individuals with insight into the health state will be recruited into the vignette development process. This will consist of several patient-representatives, who have experienced hysterectomy (for a variety of indications), and endometrial cancer. They will be recruited via established clinical networks, patient-public-involvement groups who work with Queen Mary University of London, and/or charities such as Lynch syndrome UK and others. We will also recruit several clinical experts with experience in managing patients after hysterectomy, who may be gynaecologists, or other clinicians including nurses. These will be recruited via established clinical/academic networks. These patient-representatives and clinical experts will be interviewed, individually or as one or more groups, to obtain evidence to inform vignette content.

The number of vignettes and the descriptions of health states within the vignette will be determined by evidence obtained from the literature review and clinical/patient experts, to match that required by the economic model. The length and level of detail of each vignette will be determined by this process. The vignette(s) will be formatted and worded in such a way as to be easily comprehensible. After initial development, the vignette(s) will be further reviewed by the patients and clinical experts, to ensure they clearly describe a typical experience with this health state, and refined accordingly.

The vignette(s) will then be piloted on a small number of individuals who were not previously involved in their development. These participants will be recruited via the above channels of patient and public involvement groups, charities, support groups, and/or via commercial polling companies. The aims of this pilot are to ensure vignettes are comprehensible, the task is understood, and the number of vignettes and time taken to complete the task is not too great. Following this process, the vignette(s) will be further refined as required.

7.2.2. Part 2B: Questionnaire 2: EQ-5D valuation of vignette(s)

Following the development of questionnaire 2, a substantial amendment will be submitted for permission to use this questionnaire for research purposes.

7.3. Part 3

Design: Development of an experimental survey study

This part of the study will develop a questionnaire which is designed to evaluate the **prospective acceptability of risk-reducing hysterectomy and other prevention strategies**, at varying levels of lifetime risk of endometrial cancer.

A flowchart for part 3 is given in section 9.5.3.

7.3.1. Part 3A: Development of Questionnaire 3

Questionnaire 3 will be developed in a process similar to that of previously published work. (62) We have previously undertaken research and published on acceptability of ovarian cancer prevention at different ovarian cancer risk thresholds (60).

A draft of questionnaire 3 will be developed following a literature review. This will then be reviewed by experts in the field of gynaecology/ gynaecological oncology/ gynaecological cancer prevention/ psychology, who will be recruited via established clinical/academic networks. This will also be reviewed by patient representatives, recruited in a similar manner to that described previously, via established clinical networks, patient-public-involvement groups who work with Queen Mary University of London, and/or charities such as Lynch syndrome UK and others.

The questionnaire will provide some background information on endometrial cancer, and management strategies for prevention (including lifestyle changes, hormonal treatments such as the levonorgestrel intrauterine system (LNG-IUS), and RRH). It will also contain one of a number of scenarios, describing the results of a hypothetical test, giving a certain lifetime risk of endometrial cancer. The questionnaire will then ask questions around the acceptability of the different risk-reducing interventions (for that given risk level). Following this there will be background questions on socio-economic status and medical history. It will also contain a validated measure of anxiety and cancer worry, such as the Hospital Anxiety and Depression Scale, and the Cancer Worry Score respectively, as well as questions on perceived response efficacy. There may be other questions as deemed necessary by the development process.

The number of scenarios, and the lifetime risk levels within each scenario, will be determined following the economic modelling which takes place after parts 1 and 2. This economic modelling will determine at what level of lifetime endometrial cancer risk various interventions are effective and cost-effective. This study will then examine acceptability of those interventions at and around those risk levels. Questionnaire 3 will be developed in accordance with this process described above, with input from clinical and patient experts. This will then be piloted on a small number of individuals not previously involved in their development. These participants will be recruited via the above channels of patient and public involvement groups, charities, support groups, and/or via commercial polling companies. The aims of this pilot are to ensure that materials are comprehensible and easy to use. Following this process, there may be further refinement as necessary.

7.3.2. Part 3B: Questionnaire 3: Acceptability of risk-reducing hysterectomy

Following the development of questionnaire 3, a substantial amendment will be submitted for permission to use this questionnaire for research purposes.

7.4. Questionnaire structure

7.4.1. Study Part-1: Questionnaire 1 Structure

Paper/electronic questionnaires will be identical, and participants will be required to complete one format of the questionnaire of their choosing. The questionnaire will be completed at one-time point, to reflect the cross-sectional study design. Upon completion there will be no further responsibilities.

Questionnaires will contain the following sections;

- Lynch Syndrome and health
- EQ-5D-5L questionnaire (63, 64) for participants' current HRQoL
 - Consists of two sections: EQ-5D-5L descriptive system and the visual analogue scale. It has five dimensions: mobility, self-care, activities of daily living, pain and mood disturbance. Participants are asked to indicate their health state on a five-point Likert scale.
- EQ-5D-5L questionnaire (63, 64) for participants' HRQoL 4 months after their RRH (for participants who have undergone RRH)
- Cancer Worry Scale (65)
 - The 4 items of the CWS are rated on a 4-point Likert scale ranging from "never" to "almost always." Scores range from 4 to 16. Higher scores indicate more frequent worries about cancer (66). The Cancer

Worry Score has been validated for use in Hereditary Cancer Syndrome Context with a Cronbach-alpha from 0.88 to 0.89 (66).

- Medical and family history
- Demographic information

7.4.2. Study Part 2: Questionnaire 2 Structure

This questionnaire will be designed in order to be completed electronically, and at one-time point.

It will consist of one or more vignettes describing the quality-of-life of a person following RRH. Participants will be asked to complete the EQ-5D-5L for each vignette. They may also be asked to complete a self-EQ-5D-5L, and relevant demographic and personal medical information.

The exact structure of the questionnaire will be finalised following the process described in part 2A. A substantial amendment will be submitted following development of this questionnaire, for permission to use in generating research data.

7.4.3. Study Part 3: Questionnaire 3 Structure

This questionnaire will be designed in order to be completed electronically, and at one-time point.

It will consist of a hypothetical scenario, where participants are asked to imagine that that they have had personalised EC risk-prediction, with the results being expressed as a lifetime risk of developing EC. It will be stressed that this testing and results are fictional, and do not arise from real-world testing of participants.

They will then be given accurate, truthful information on EC risk-reducing management options, including lifestyle advice, the LNG-IUS, and RRH, and their benefits and risks. It will be stressed that this testing and results are fictional, and do not arise from real-world testing of participants.

They will then be presented with a number of scenarios, describing the hypothetical results of this test, and asked which risk-reduction management options they would be willing to consider if they were faced with such results in reality.

The exact structure of the questionnaire will be finalised following the process described in part 3A. A substantial amendment will be submitted following development of this questionnaire, for permission to use in generating research data.

8. Study population

8.1. Inclusion criteria

Part 1:

- Diagnosis of Lynch Syndrome (confirmed germline mutation in *MLH1*, *MSH2*, *MSH6*, *PSM2*, *EPCAM*)
- ≥18 years
- Female
- UK resident
- Able and willing to provide informed consent

For part 1, eligible participants will be adult women with LS living in the UK. This is to reflect the full range of views and experiences from this group, including from different age groups.

8.2. Exclusion criteria

Part 1:

- Unwilling or unable to provide informed consent
- Inability to understand written and verbal English
- Prior history of endometrial, ovarian or cervical cancer

Participants are excluded if they are unable to provide written informed consent in English, or if they have a prior history of gynaecological cancer for which the treatment is hysterectomy (which includes endometrial, ovarian and cervical cancer). This is because such cancer precludes them from having had or considering a risk-reducing hysterectomy.

9. Study procedures

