The UK's National Institute for Health and Care Excellence (NICE) recommends economic decision models should use HRUS to calculate guality-adjusted life years (QALYs) (33). In their guidance on the evaluation of health technologies, NICE recommends such models be based upon the "reference case", to ensure a consistent approach to health-economic modelling across multiple diseases and technologies (34-36). The preferred instrument is the EQ-5D; a generic patientreported-outcome measure developed by the EuroQol Group, which assesses quality of life using five domains; mobility, self-care, usual activities, pain/ discomfort, anxiety/depression (37). This questionnaire was originally available with three levels of response for each domain (known as EQ-5D-3L), although a version with fivelevels of response has been developed, allowing for finer discrepancy between health states (known as EQ-5D-5L, hereafter referred to as EQ-5D) (38). EQ-5D ratings are converted to HRUS using a country-specific formula, derived from a timetrade-off exercise conducted on a representative sample of the general population for each country (39). Thus the "reference case" provides for patient-reported outcomes to be converted to HRUS using the valuations of society.

Understanding the impact of RRH-BSO on HRQoL would enable clinicians to better support women with increased EC risk contemplating risk-reducing surgery in a complex decision making process. Additionally, the derivation of HRUS would enable more accurate health-economic and cost-effectiveness analysis of risk reducing surgery to prevent EC. Disutility is a key variable and driver which can affect the results of these analysis. It is currently unknown what level of lifetime EC risk would justify risk-reducing treatments, although such modelling has been undertaken for risk-reducing BSO in OC prevention (40, 41).

The aim of this research would be to obtain HRUS for pre and post-menopausal patients undergoing RRH for EC prevention. This can then be used to build decision analysis models to define the EC lifetime risk threshold at which to perform RRH.

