RRH without bilateral oophorectomy is not commonly performed, as national guidelines recommend that women with LS have RRH-BSO to protect them from their additional OC risk (50) (51). There may be a small number of LS women who have received RRH alone without bilateral oophorectomy outside of recommended practice. Whilst these women would be valuable in obtaining HRUS for this procedure, they would be expected to have some additional risk of anxiety from their remaining risk of ovarian and colorectal cancer. Whilst there are numerous risk factors for EC, few patients other than those with LS undergo RRH (52), and so there is no major cohort of patients who have received RRH alone (for cancer prevention) without bilateral oophorectomy, and who are now free from an elevated risk of any other cancer.

Due to the rarity of this target patient cohort, it is challenging to perform a prospective EQ-5D study for patients undergoing this procedure. Where EQ-5D ratings are not available for a specific treatment or condition, due to rarity or other factors, NICE recommends alternatives, including the use of the closest available "proxy conditions", and vignettes (36, 53). People with LS represent the best available target patient population for the development of HRUS for EC preventive surgery. However, it is necessary to use a separate methodology for pre-menopausal patients undergoing RRH without bilateral oophorectomy. A preferred study design is the development of vignettes describing the treatment and condition of interest, which is then rated using EQ-5D by the general population or patients with similarities to the condition. This provides the closest match to the NICE reference case (54).

This study will therefore obtain EQ-5D ratings of risk reducing surgery for endometrial cancer via two related approaches:

- A cross-sectional EQ-5D study of women with LS, including those who have undergone RRH ± BSO and those who have not (controls). This will enable HRUS for RRH to be obtained, including for pre and post-menopausal patients undergoing RRH-BSO.
- 2) A vignette-based study of pre-menopausal RRH without bilateral oophorectomy (for a patient with no remaining cancer risk). This will be valued by members of the general population using EQ-5D ratings.

Acceptability of risk-reducing strategies

Prior to clinical utilisation, it is necessary to determine if risk-reducing surgery is acceptable to women in the target population.

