10.2. Method of analysis

Baseline characteristics will be calculated using descriptive statistics. Appropriate statistical tests will be used. Chi-square tests will be used to compare categorical

variables and t-Test (parametric) and Mann-Whitney (non-parametric) tests to compare continuous outcome variables between two groups. Appropriate Logistic/ Linear regression models will be used to evaluate impact of covariates on Linear outcome variables. The data set will be subject to two analysis formats to minimise the risk of bias during interpretation. Initially by cohort-matching, to reduce the influence of confounding variables. Secondly by regression analysis to analyse the impact of covariates of the categorical and linear variables. All analysis will be performed on R (R Core Team, Foundation for Statistical Computing, Vienna, Austria), or equivalent software package.

A Markov model built in TreeAge software (TreeAge, Williamstown, MA) will form the basis of an economic evaluation on the cost-effectiveness of RRH for endometrial cancer risk threshold at which to perform surgical prevention (hysterectomy) or other non-surgical preventive interventions (such as the levonorgestrel-intrauterine system, or other chemo-prevention) for endometrial cancer risk. Models will be built in order to evaluate lifetime costs as well as effects with undertaking 'risk reducing hysterectomy' in premenopausal and postmenopausal women by comparing it with 'no risk reducing hysterectomy' at varying levels of endometrial cancer risk. Additional modelling will also evaluate lifetime costs as well as effects as well as effects of endometrial cancer risk. Additional modelling will also evaluate lifetime costs as well as effects of endometrial cancer risk. Additional modelling will also evaluate lifetime costs as well as effects of endometrial cancer risk. Additional modelling will also evaluate lifetime costs as well as effects with undertaking non-surgical preventive interventions in premenopausal and postmenopausal women by comparing it with 'no intervention' at varying levels of endometrial cancer risk. The analysis will be undertaken primarily within the UK National Health Service (NHS) context. We will also explore the impact of outcomes in other health systems.

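### Women whose uterus was removed for a non-risk-reducing indication are eligible for Part 1 and fall among the controls, which contaminates the predictors-of-RRH analysis and any RRH versus no-RRH utility comparison

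*Protocol*

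**What the plan says.** Eligibility for Part 1 is broad. Section 8.1: "For part 1, eligible participants will be adult women with LS living in the UK". Apart from consent and language, the only exclusion in section 8.2 is "Prior history of endometrial, ovarian or cervical cancer". The reason given there is: "This is because such cancer precludes them from having had or considering a risk-reducing hysterectomy". No criterion concerns hysterectomy or oophorectomy done for any other reason.

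The comparator is described in section 5.2, where the Part 1 sample is women with LS "including those who have undergone RRH ± BSO and those who have not (controls"). Section 5.1 describes RRH as an operation to prevent endometrial cancer, so a hysterectomy for benign disease is not RRH.

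The primary endpoint (section 6.3) is "Utility Scores for risk-reducing hysterectomy". A secondary endpoint (section 6.4) is "Variables predictive for risk-reducing hysterectomy". On the economic model, section 5.1 says: "Disutility is a key variable and driver which can affect the results of these analysis".

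Section 10.2 plans two analyses. The first is matching ("Initially by cohort-matching, to reduce the influence of confounding variables") and the second is covariate regression. It names neither prior surgery as a variable nor a restriction to women who could have had RRH. Section 7.4.1 lists a medical and family history section in Questionnaire 1 without giving its items.

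**The concern.** The exclusion rests on a principle: a woman who cannot have had or consider RRH does not belong in the study. The protocol applies it to uterus loss through gynaecological cancer and to no other route. A woman who had a hysterectomy for benign disease, or as part of other surgery, has no uterus and no remaining decision about RRH. She is nevertheless eligible and sits on the no-RRH side.

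Two analyses are exposed:

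- **Predictors of RRH.** She is counted as a woman who did not take up an operation that was not open to her.
- **Utility comparison.** If women with RRH are compared with those without, to obtain the disutility for the model, the no-RRH group contains women who have had a hysterectomy.

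Matching and regression balance covariates among women who could be in either group. They cannot make a woman without a uterus a candidate for RRH; only a restriction can.

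**Working it through.** **1. Classification under the text.** Take an adult UK woman with LS, no gynaecological cancer, and a hysterectomy for benign disease.

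- Section 8.1: meets the inclusion criteria.
- Section 8.2: meets no exclusion criterion, although the stated reason for the cancer exclusion describes her.
- Section 5.2: has not undergone RRH, so she is a control.
- Section 10.2: nothing removes or separates her.

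**2. Number of controls.** Section 10.1 gives 250 women with RRH among 750 respondents (limits 100 of 300 and 400 of 1,200). Controls: 750 - 250 = 500 (limits 200 and 800). Applying the 30% uptake from the same section would give 0.70 × 750 = 525, which makes no practical difference. If f = 10% of 500 controls were affected, that would be 50 women. The protocol gives no value for f, so this is an illustration.

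**3. Effect on a utility difference.** Let d be the true decrement (RRH versus women with a uterus), f the share of controls without a uterus for other reasons, and r their decrement relative to that of RRH. The control mean is lowered by f × r × d, so

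observed decrement = d × (1 - f × r).

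All values of f and r are assumptions. The share of the true decrement that is observed is:

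| f | r = 0.5 | r = 1 | r = 1.5 |
|---|---|---|---|
| 5% | 97.5% | 95% | 92.5% |
| 10% | 95% | 90% | 85% |
| 20% | 90% | 80% | 70% |

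With r = 0 there is no distortion. With r < 0 (these women feel better than other controls) the decrement is exaggerated; for example, f = 10% and r = -0.5 gives 105%.

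**4. Effect on a predictor of RRH.** Assume a binary predictor present in 60% of women with RRH and 40% of true controls. The true odds ratio is (0.6/0.4)/(0.4/0.6) = 2.25. With f = 10% and prevalence p among the misplaced women, prevalence among all controls is 0.9 × 0.4 + 0.1 × p:

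- p = 40%: 0.400, odds ratio 2.25 (unchanged)
- p = 60%: 0.420, odds ratio 1.5/(0.420/0.580) = 2.07
- p = 75%: 0.435, odds ratio 1.5/(0.435/0.565) = 1.95
- p = 20%: 0.380, odds ratio 1.5/(0.380/0.620) = 2.45

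The direction depends on who these women are.

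**5. Primary endpoint.** It is a utility level measured in women who had RRH. The composition of the control group does not enter it.

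**The case against.** The strongest reply has four parts.

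- **The word controls is a gloss in the Rationale, not an analysis-set definition, and analysis sets may be settled in a statistical analysis plan that is not shown.** This has some force. But eligibility, the reason for the exclusion and the description of controls are all protocol text, and they are inconsistent with one another as they stand.
- **The data may already be collected.** Section 7.4.1 has health and medical history sections, and the second EQ-5D goes only to women who had RRH, so RRH status must be asked. This stands: the protocol does not show that indication or organs removed are missing. It does not show that they are recorded either, and with one questionnaire and no follow-up (section 9.7) there is no planned way to recover them.
- **Broad recruitment is deliberate.** Section 8.1 says so. That is compatible with the point, since separating these women at analysis is enough.
- **The protocol does not state that the LS controls supply the no-RRH utility in the model.** This is correct. Section 10.2 says only that utility data come from this survey. The utility part therefore applies to any RRH versus no-RRH comparison that is made, while the predictor endpoint is affected directly.

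A reader might infer that the decrement is certainly understated. The documents do not support that: it requires these women to share the RRH decrement, and relief of symptoms after benign surgery could remove or reverse the bias.

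A reader might also want women with oophorectomy alone removed from the controls altogether. They still have a uterus and can consider RRH, so the reason in section 8.2 does not reach them and they belong in the predictor analysis. They matter only as a comparator for utility after RRH with oophorectomy, and only if the oophorectomy was bilateral and pre-menopausal. Section 5.2 places the major distinction there and expects no added disutility from oophorectomy after menopause.

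**Conclusion.** The point holds as an inconsistency in eligibility and in the comparator. The protocol's own reason for exclusion covers women who lost the uterus for another indication, but they are admitted and, on the wording of section 5.2, counted as controls. The predictors-of-RRH analysis and any RRH versus no-RRH utility comparison are contaminated to the extent that such women respond.

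The size cannot be estimated from the protocol. With r = 1 and f between 5% and 20%, both assumed, a utility decrement would appear at 95% to 80% of its true value; with other values of r the bias could be smaller, larger, absent or reversed. An odds ratio for a predictor can move either way or not at all.

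A reader might take this as a threat to the primary endpoint. It is not, because that endpoint is a utility score in women who had RRH.

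**What to change.** In sections 8.2 and 10.2:

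- Define controls as women with LS with the uterus in situ at the time of the survey.
- Restrict the predictors-of-RRH analysis to women who had RRH or still have a uterus.
- Exclude women with hysterectomy for a non-risk-reducing indication from both comparisons, or tabulate them as a separate group.
- For the utility comparison only, treat pre-menopausal bilateral oophorectomy without hysterectomy as its own category. Keep these women in the predictor analysis.
- Confirm that Questionnaire 1 records, for any hysterectomy or oophorectomy, the indication, the date and the organs removed. Add an item if it does not.

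The cost is at most one questionnaire item, an analysis-set rule, and some loss from the larger group. With 250 women with RRH, going from 500 to 450 controls (assumed f = 10%) multiplies the standard error of a difference in means, at equal variances, by √[(1/250 + 1/450)/(1/250 + 1/500)] = 1.018. Going to 400 (f = 20%) multiplies it by √[(1/250 + 1/400)/(1/250 + 1/500)] = 1.041. The loss of precision is about 2% to 4%.
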